At each site, eligible subjects will be identified consecutively as they attend scheduled clinical appointment with their physician (Day 1). Upon written consent, data regarding disease activity, treatment patterns, burden of disease and quality of life will be collected from medical records and PRO tools, including quality of life (SF-36, EQ-5D and IBDQ) and work productivity (WPAI) questionnaires. Retrospective data will refer to the previous three years and will include the previous er 4. er 4. applica IBD treatments (drug, dose, treatment duration, drug changes, surgeries), and use of other healthcare resources related with the management of IBD.

1st quarter 2018

1st quarter 2018

3rd quarter 2019

1st quarter 2

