### 2.2.2 Secondary endpoints

- Distribution of age, gender, smoking habits, professional status, family history, educational level, subject income by IBD type.
- Distribution of clinical variables (steroid behaviour, anthropometric information, medical history and comorbidities, clinical characterization of disease) by BD type.
- Therapies for IBD (aminosalicylates, steroids, immunomodulators, immunosupressors biologics, antibiotics, probiotics and surgeries) and the length of these therapies during the previous 3 years. Property of Taked

Proportion of biologic-experienced patients.

Proportion of patients who have not responded previously to biologic therapies and reason.

- IBD treatment introduced at Day 1 (if applicable).
- Socio-demographic, clinical and treatment-related variables in patients with moderate to severe activity of CD (HBI score  $\geq$  8 or CDAI score  $\geq$  220 points) versus patients with mild or no activity (HBI score < 8 or CDAI score < 220 points).

- Socio-demographic, clinical and treatment-related variables in patients with moderate to severe activity of UC (9-point partial Mayo score ≥5) versus patients with mild or no activity (9-point partial Mayo score <5).
- Mean score of EQ-5D by IBD type.
- Mean score of different components of SF-36 by IBD type.
- Mean total score of IBDQ and by domain (bowel symptoms, systemic symptoms, emotional function and social function). Patients with ostomy will a in the applicable not be evaluated since this questionnaire is not validated to be used in this population.
- Mean total percentage of work impairment (WPAI).
- Mean work time missed (WPAI).
- Mean impairment while working (WPAI).
- Mean total activity impairment (WPAI).
- Healthcare resources (previous 3 years): drug therapies, imaging and laboratory testing, surgeries, hospitalizations and consultations. y and sul

### STUDY DESIGN 3

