This is a multicenter, non-interventional, cross-sectional study (Figure 1) aiming primarily to determine the rate of control of IBD activity (Crohn's Disease [CD] or Ulcerative Colitis [UC]). At each center, eligible subjects will be identified consecutively as they attend a scheduled clinical appointment with their physician (Day 1). Upon written consent, data regarding disease activity, treatment patterns, burden of disease and quality of life will be collected from the patients' medical records and administered Patient Report Outcome (PRO) questionnaires, including quality of life (SF-36, EQ-5D and IBDQ) and work productivity (WPAI) questionnaires. Besides the cross-sectional data collection, the study will have an additional retrospective data collection referring to the three years previous to Day 1, regarding the previous IBD treatments (drug, dose, treatment duration and drug changes), and use of other healthcare resources related with the management of IBD. Property of

Day 1

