BMI categories (in the previous 3 years, not considering Day 1) - The BMP (in the and subject to the at previous 3 years, not considering Day 1) will be recoded according to the following cut-offs:

Underweight – BMI <18.50 kg/m^2

Normal range – BMI between 18.50 and 24.99 kg/m^2

Overweight – BMI between 25.00 and 29.99 kg/m^2

Obese – BMI  $\geq$  30.00 kg/m^2

Total number of fecal calprotectin levels per patient - For each patient, fecal calprotectin levels in the previous 3 years will be calculated by the mean of all fecal calprotectin levels collected in that period.

Fecal calprotectin results suggestive of inadequate activity control at least one time -A dichotomous variable (yes/no) will be calculated:

Yes – Patients with at least one fecal calprotectin suggestive of inadequate control of activity collected in the previous 3 years.

Patients without fecal calprotectin suggestive of inadequate control of activity collected in the previous 3 years.

Colonoscopy results suggestive of inadequate activity control - A dichotomous variable (yes/no) will be calculated:

Yes – Patients with at least one colonoscopy suggestive of inadequate control of activity collected in the previous 3 years.

No – Patients without colonoscopy suggestive of inadequate control of activity collected in the previous 3 years.

Total number of previous imaging and laboratory testing due to IBD per patient – Sum of all previous imaging and laboratory testing due to IBD for each patient, in the previous 3 years.

**Classes of IBD therapy** – IBD therapies during the previous 3 years will be recoded according to the following categories:

Salicylic derivates: 1.1. sulphassalazine (SSZ), 1.2 Mesalazine (5-ASA), 1.3 Olsalazine and 1.4 Mesalazine extended release.

Corticosteroids: 2.1 Hydrocortisone, 2.2 Prednisone, 2.3 Prednisolone, 2.4 Budenoside and 2.5 Methylprednisolone.

Immunosuppressors: 3.1 Azathioprine, 3.2 6-Mercaptopurine, 3.3 Methotrexate, 3.4 Cyclosporine and 3.5 Tacrolimus.

Biologic therapy: 4.1 Infliximab, 4.2 Adalimumab, 4.3 Vedolizumab, 4.4 Certolizumab, 4.5 Golimumab and 4.6 Ustekimumab.

Antibiotics: 5.1 Metronidazole and 5.2 Ciprofloxacin.

Nutritional support: 6.1 Enteral nutrition and 6.2 Parenteral nutrition.

Others: rest of the IBD therapies.

Frist treatment start/change after moderate to severe IBD diagnosis per patient – A dichotomous variable (yes/no) will be calculated:

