Yes – Patients with at least one IBD treatment (just IBD class of salicylic derivates, corticosteroids, immunosuppressors or biologic therapy) with end date equal to Day 1 date and reason for end of IBD treatment classified as "Dose changed".

No – Patients without any IBD treatment (just IBD class of salicylic derivates, corticosteroids, immunosuppressors or biologic therapy) with end date equal to Day 1 date and reason for end of IBD treatment classified as "Dose changed".

Total number of IBD treatments during retrospective period (previous 3 years and at Day 1) per patient – Sum of IBD treatments reported during retrospective period (3 years) for each patient in the previous 3 years and including IBD treatment starting at Day 1.

**IBD treatment duration** – Time between the beginning of the IBD treatment until the end of the treatment (in months). For patients with ongoing IBD treatment at Day 1, stop date will be considered as Day 1 date visit.

**Salicylic derivates treatment duration per patient** – Sum of all IBD salicylic derivate treatments duration for each patient (in months). If the patient has two IBD salicylic derivate treatments taking in simultaneous, it will only be considered the treatment with the longest duration.

**Corticosteroids treatment duration per patient** – Sum of all IBD corticosteroid treatments duration for each patient (in months). If the patient has two IBD corticosteroids treatments taking in simultaneous, it will only be considered the treatment with the longest duration.

IS OF USE

Immunosuppressors treatment duration per patient - Sum of all IBD immunosuppressor treatments duration for each patient (in months). If the patient has two IBD immunosuppressors treatments taking in simultaneous, it will only be considered the treatment with the longest duration.

Biologic therapy treatment duration per patient - Sum of all IBD biologic therapy treatments duration for each patient (in months). If the patient has two IBD biologic therapies taking in simultaneous, it will only be considered the treatment with the longest duration

Antibiotics treatment duration per patient - Sum of all IBD antibiotic treatments duration for each patient (in months). ,ct to

Nutritional support treatment duration per patient - Sum of all IBD nutritional support snd treatments duration for each patient (in months).

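### Treatment duration by class: the longest-of-two rule miscounts partly overlapping courses, the antibiotic sum counts concurrent courses twice, and no cut at the start of the 3-year window is stated

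*SAP*

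**What the plan says.** SAP section 2.2.2 makes treatment exposure a secondary endpoint: a list of therapies that ends "antibiotics, probiotics and surgeries) and the length of these therapies during the previous 3 years". The protocol has the same endpoint (sections 1.4 and 10.1.1).

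SAP section 9 supplies the derivation:

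- **Single course.** Duration is "Time between the beginning of the IBD treatment until the end of the treatment (in months"). A treatment still ongoing is stopped at Day 1. Nothing is said about a course that began before the 3-year period.
- **Salicylates, corticosteroids, immunosuppressors, biologics.** Course durations are summed per patient, with an exception for concurrent use, worded alike in all four classes. For biologics: "If the patient has two IBD biologic therapies taking in simultaneous, it will only be considered the treatment with the longest duration".
- **Antibiotics, nutritional support, other treatments.** Durations are summed, with no provision for concurrent use. The antibiotic class holds two drugs ("5.1 Metronidazole and 5.2 Ciprofloxacin"). The Others class is the "rest of the IBD therapies", so probiotics, which the endpoint names but no listed class contains, fall there.

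On the window, SAP section 3 describes retrospective collection "referring to the three years previous to Day 1, regarding the previous IBD treatments (drug, dose, treatment duration and drug changes"). Protocol section 6 says "Retrospective data will refer to the previous three years". The class definitions in SAP section 9 state that "IBD therapies during the previous 3 years will be recoded". SAP section 8.2 names treatment duration as an example of a quantitative variable to be compared between patients with and without active disease.

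**The concern.** The exception for concurrent use covers two treatments and does not say what counts as simultaneous. When one course starts shortly before another ends, a programmer must either treat the pair as simultaneous and discard the shorter course, or treat it as not simultaneous and add both. The first loses real time on treatment; the second counts the shared time twice. The same records can therefore yield two reported durations, with errors in opposite directions.

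The definition matters for another reason. SAP section 9 treats a dose change as a possible reason for the end of a treatment, which suggests that one drug may be stored as several adjoining records. Whether records that share a date are simultaneous is not stated.

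For antibiotics there is no guard against double counting at all. Separately, without a stated cut at the start of the window, a class duration may include time before the three years that the endpoint names. It would then partly reflect how long the patient has had the disease, which section 8.2 tests as its own variable.

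**Working it through.** The documents give no duration figure to reproduce, so I applied the section 9 rules to constructed histories. Month 0 is 36 months before Day 1 and month 36 is Day 1. The histories are mine; the documents do not say how often such patterns occur.

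**Formulas.** A course from s to e has length d = e − s. For two courses with overlap o:

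- longest only: L = max(d1, d2)
- plain sum: S = d1 + d2
- time on the class (union): U = d1 + d2 − o

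So L − U = −(d_short − o) and S − U = +o. The longest-only reading is exact only when the shorter course lies wholly inside the longer (o = d_short). The sum is exact only when there is no overlap (o = 0). For any partial overlap, 0 < o < d_short, neither equals time on the class.

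**Two courses in one of the four classes (months)**

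| Courses | d1, d2 | o | Longest only | Sum | Union |
|---|---|---|---|---|---|
| 0-18, 17-36 | 18, 19 | 1 | 19 | 37 | 36 |
| 0-12, 9-36 | 12, 27 | 3 | 27 | 39 | 36 |
| 0-18, 12-36 | 18, 24 | 6 | 24 | 42 | 36 |
| Nested: 0-36, 10-16 | 36, 6 | 6 | 36 (rule applies) | – | 36 |
| Sequential: 0-16, 18-36 | 16, 18 | 0 | – | 34 (rule applies) | 34 |

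In the first row, a one-month overlap at a switch costs 36 − 19 = 17 months under the longest-only reading and adds 1 month under the sum.

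**Three courses.** Take 0-12, 11-24 and 23-36, with lengths 12, 13 and 13 and two overlaps of 1 month. The union is 38 − 2 = 36. The SAP rule speaks of two treatments, so the result depends on how it is extended. Keeping one course gives 13, dropping only the middle course gives 12 + 13 = 25, and summing gives 38. None of these is the rule's answer, because the rule does not define one.

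**Antibiotics (plain sum).** Two courses over months 10-12: 2 + 2 = 4, union 2. Courses 10-12 and 11-13: 2 + 2 = 4, union 13 − 10 = 3.

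**Start of the window.** This part assumes that the CRF records true start dates and that the endpoint means time inside the window. An ongoing drug started 12, 24 or 60 months before month 0 then gives 36 + 12 = 48, 36 + 24 = 60 or 36 + 60 = 96, against 36.

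**The case against.** **The target is assumed.** The documents never say that class duration means the union of intervals. That is true. But the four-class rule exists to stop concurrent time being counted twice, and it returns the union for nested and for sequential courses. Time on the class is the quantity it appears to aim at, and partial overlap is where it misses.

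**Partial overlap may be rare.** SAP section 9 records switches and drug changes as decisions at an appointment, which fits end-to-end records. This stands as a limit on size: no frequency is given.

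**A sum is a legitimate quantity.** For the mixed Others class this is right; a sum of drug-months is well defined and needs only a label. For antibiotics it is weaker. The endpoint names them and asks for length of therapy, and the class contains two drugs that could be given together.

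**The window may already be enforced.** A reader might infer from section 9 that time before the window is certainly counted. The documents do not support that. The CRF and the table shells are not available here, SAP section 3 lists treatment duration among the three-year data, and a CRF that records starts only from the window edge would leave no error. The endpoint wording could also mean the full course length of therapies used in the window. What remains is that section 9 cuts at Day 1 and states no cut at the other end.

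**Only descriptive results are involved.** Protocol section 10.5 calls all analyses descriptive, and SAP section 8.2 mentions treatment duration only as an example, without saying that the class totals are what is tested. This limits the consequence but does not make the durations correct.

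**Conclusion.** The concern holds for overlap. As written, the four-class rule gives a wrong class duration whenever two courses partly overlap, by d_short − o months too few or o months too many depending on the reading. It gives no unique result for chains of three or more. The antibiotic sum counts concurrent courses twice. This conclusion rests on reading class duration as time on the class.

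The missing cut at the start of the window is conditional. It produces totals above 36 months only if true start dates are recorded and the endpoint means time in the window. It should be confirmed rather than presumed.

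The affected results are secondary: descriptive durations and any comparison of treatment duration by disease activity. The primary proportions and the sample size do not use these variables. A reader might also expect the partial-date rule in SAP section 8 to create false overlaps. It could, but the documents give neither the gaps between courses nor the share of partial dates, so no size can be attached to it. The same holds for the overall effect in this study.

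**What to change.** 1. In SAP section 9, replace the longest-duration rule for the four classes, and the plain sum for antibiotics, with one definition: the length of the union of the patient's treatment intervals in that class. This covers partial overlap, nested courses, chains of any length and adjoining records. The same wording can serve nutritional support for consistency, although the endpoint does not list it.
2. Confirm whether the CRF already limits start dates to the retrospective period. If it does not, cut each interval to the 3-year window before merging, for the endpoint in section 2.2.2. If full course length is also wanted, report it under a separate name.
3. Label the total for the Others class as drug-months.

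The cost is a few lines of SAP text and a standard interval-merge step. Protocol section 7.2 already collects start and end dates, so no new data are needed. If the SAP is not reissued, its section 1 provides for recording the change in the statistical and study reports.

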### **10 APPENDIX**

rt: R. Fornor Property of Takeda. Fornor External document: RISE AR TLFs Version No. 1.0, 28Aug2019
